**Design and Implementation of a Nutritional Intervention in
Patients With Oropharyngeal Dysphagia**

NCT02959450

October 10th, 2021

Patients of 18 years and older, both genders, who had a primary caregiver and a confirmed diagnosis of OD were included. Eating Assessment Tool (EAT-10) and Volume- Viscosity Swallow Test (V-VST) were performed by a clinical nutritionist in order to evaluate the safety and efficacy of swallowing and confirm the diagnosis of OD; select the type of viscosity and volume appropriate for the prescription of the texture-modified diet. Patients with cancer, kidney or hepatic failure, terminally ill patients, as well as high risk of aspiration, reporting a decrease in oxygen saturation $>5\%$ in the V-VST, or with enteral nutrition (EN) through a nasoenteral tube or gastrostomy were excluded. We estimated a sample size of 50 patients per group by the formula of survival of Argimon et al , with an alpha level of 0.05 and more than 90% power to detect a difference of 15% of mortality between groups.

Anthropometry

Anthropometric measurements were performed according to the reference manual for anthropometric standardization. The same scale was used for all patients at each visit. Forearm circumference was measured at the midpoint of the right arm and calf circumference was measured in a supine position with the tape along the calf to measure the greatest circumference without compressing the subcutaneous tissue.

Mini Nutritional Assessment

The nutritional risk was assessed using the Mini Nutritional Assessment (MNA) questionnaire, a valid and reliable tool to identify malnutrition in elderly people. The original version of this tool was used for this study contained 18 questions with a maximum of 30 points. It is considered that a score lower than 17 points represents malnutrition, between 17 and 23.5 points of risk of malnutrition and more than 24 points that the patient is well nourished.

Dietary intake

For the evaluation of the quality and quantity of dietary intake, a 24-hour multiple-step recall was applied and the Food Processor Nutrition Analysis® software was used for the detailed nutritional analysis.

Body composition

The body composition was performed using a single-frequency BIA (50-kHz, Quantum X, RJL Systems, Inc) with the standard technique: all participants were supine with limbs slightly spread apart from the body, refrained from eating, drinking, and exercising for six hours, no alcohol within 24 h before testing and portable electric heaters. The area was cleaned with alcohol and the electrodes (recommended by manufacturers RJL Systems, Inc) were placed on an imaginary line bisecting the ulnar head of the right hand and on an imaginary line bisecting the medial malleolus of the right finger and on the base of the second toe of the right foot. Finally, the R and Xc values were recorded. All measurements were performed under strictly standardized conditions by the observer, using the same device in order to avoid interobserver and interdevice variability. The Quantum X was calibrated periodically by a test resistor with a known value of 495 – 505 ohms of R to ensure accuracy of measurements. The coefficient of variation was reported in a range from 1.8 to 2.9%.

Muscle strength

The muscular functionality was evaluated by a handgrip dynamometer (Takei®). The operator, using the same device in order to avoid interobserver and interdevice variability, performed all measurements under strictly standardized conditions. For the measurement, subjects were placed standing with arms outstretched parallel to the trunk taking the dynamometer and applying maximum strength with each hand without support. The measurement was repeated three times with separation of 1 min to avoid fatigue and the maximum value was recorded. The instrument was routinely checked resistors and capacitors of known values.

Nutritional intervention

Nutritional requirements for both groups were calculated based on the American Society for Parenteral and Enteral Nutrition and Society of Critical Care Medicine (A.S.P.E.N./S.C.C.M.) and recommendations of PROT-AGE Study Group as follows: 25- 30 kcal/kg Body Weight (BW)/day in patients with body mass index (BMI) <30 kg/m² and 20-25 kcal/kg ideal BW/day with BMI > 30 kg/m²; protein were

calculated 1.2-1.5 g/kg

BW/day for patients with BMI <30 kg/m² and in case that BMI was >30 kg/m² protein were calculated 2 g/kg ideal BW/day in both groups. Both groups received swallowing rehabilitation (postural maneuvers, increase oral sensitivity, neuromuscular practices).

Subjects were randomly allocated to intervention group (modified consistency diet, with a nectar or pudding viscosity) or control group (standard treatment) using a blocked allocation strategy. The *control group* received a traditional modified texture diet, with pureed foods and one viscosity of thickened drinks. The viscosity beverages were not systematically controlled. For the *intervention group* a chef and a clinical nutritionist developed the texture- modified foods and thickened drinks diet, with nectar or pudding viscosity and controlled bolus volume. The foods were thickened using Enterex Food Thickener, Victus® and the viscosity of menus was standardized and measured with a Brookfield Viscometer (model RV). The menus with nectar consistency had a viscosity of 51-350 centipoises (cP) and the pudding consistency foods with a higher viscosity at 1,750 cP. The viscosity of the diet was prescribed according to the viscosity and volume tolerated in the V-VST. A recipe book for caregivers and patients was made to facilitate the preparation of the diet with the exact amount of thickener to use in each menu to achieve the desired viscosity. Training was also provided to patients and caregivers by a video on the use of food thickener (modified ediblestarch) on each menu.

The primary outcome was the amount of energy (kcal/kg) and protein (g/kg) consumed, the secondary outcome was body composition and muscular functionality. The follow-up was carried out in 5 visits during 12 weeks. Adherence to the prescribed meal plan was evaluated at each visit. To evaluate the adherence, it was necessary to have an intake of more than 80% of the nutritional requirements with 24-hour recall. If the intake was lower than indicated, oral nutritional supplements were prescribed to meet the nutritional requirements established in both groups.

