**Design and Implementation of a Nutritional Intervention in
Patients With Oropharyngeal Dysphagia**

NCT02959450

October 10th, 2021

Statistical analysis

The data are presented as mean \pm standard deviation or median with interquartile range [25th- 75th percentile], depending of data distribution. The Shapiro-Wilk test for proper parametric or non-parametric test was performed. Differences between groups at baseline were evaluated with Student's t-test or U Mann-Whitney test for continuous variables and proportions were compared using the Chi2 or Fisher test. Two analyses were performed to evaluate the effect of the nutritional intervention: an intention-to-treat analysis (considering all of the participants) and per-protocol analysis (considering participants who finished the follow-up). Missing data were imputed with the multivariate imputation. For the intention- to-treat analysis, we imputed five complete data sets and pooled the results for the analysis. For post-intervention comparison within-groups, a paired Student-t or Wilcoxon matched-pairs signed rank tests were performed. Also changes between baseline and final intervention in oral intake, body weight and HGS were obtained between groups and were compared with the Mann-Whitney U test, according to the nonparametric distribution of the data. A p-value <0.05 was considered statistically significant. The data were analyzed using the Statistical Package for the Social Sciences (SPSS®) version 25.

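### The calibration check given for the dynamometer cannot verify force and is probably misplaced, and the SAP names no between-group comparison of change in body composition

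*Protocol*

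**What the plan says.** The Muscle strength section of the Protocol names one device: "The muscular functionality was evaluated by a handgrip dynamometer (Takei". It requires a single device and operator under standardised conditions, and then ends with "The instrument was routinely checked resistors and capacitors of known values". A word such as 'with' seems to have dropped out. No known weight or other force standard is mentioned anywhere in the Protocol or SAP.

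The Body composition section concerns the single-frequency impedance analyser. Two quantities are taken from it: "Finally, the R and Xc values were recorded". The check given there is that "The Quantum X was calibrated periodically by a test resistor with a known value of 495 – 505 ohms of R". The next sentence adds a precision figure, "The coefficient of variation was reported in a range from 1.8 to 2.9" percent, without saying whether it covers R, Xc or a derived value.

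The Protocol makes energy and protein intake the primary outcome, and body composition and muscular functionality secondary. The SAP states: "For post-intervention comparison within-groups, a paired Student-t or Wilcoxon matched-pairs signed rank tests were performed". It then describes a between-group comparison of change by the Mann-Whitney test and lists three variables for it: oral intake, body weight and handgrip strength (HGS). Body composition is not on the list.

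**The concern.** A resistor or capacitor applies no force, so the check as placed says nothing about whether the dynamometer reads grip strength correctly. In the impedance paragraph, a resistor has essentially no reactance, so it can verify R but not a non-zero Xc. The one sentence that mentions capacitors is attached to a device on which they have no use.

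This matters because of how the SAP uses the measurements. If a device drifts between baseline and week 12, the drift becomes part of each patient's change. Randomised groups measured over the same period share it, so a comparison of change between them is largely unaffected. A within-group pre-post test has no such protection: it cannot separate treatment effect from drift, or from natural recovery, the rehabilitation given to both groups, or any other time trend. For HGS the SAP provides both kinds of test. For body composition it names only the exposed kind.

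**Working it through.** **1. Two readings of the calibration sentence**

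| Reading | Force check of dynamometer described? | R check described? | Xc check described? |
|---|---|---|---|
| The sentence refers to the dynamometer, as placed | No: electrical standards only | Yes: test resistor | No |
| The sentence was displaced from the impedance paragraph | No: nothing remains | Yes: resistors | Yes: capacitors |

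The force column is the same on both readings. The Xc column depends on which is right. The second reading is the more likely, because the impedance analyser is the only device in these sections that measures electrical quantities. The documents do not settle it.

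The resistor range of 495 to 505 ohms is 500 ± 5 ohms, and 5/500 = 1.0%. It concerns R only. The coefficient of variation describes repeatability, not accuracy, so it does not fill the gap for Xc.

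**2. Which errors reach which test**

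Write a reading as a + b × true value.

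- Constant offset a: cancels in change from baseline, so both kinds of test are unaffected.
- Constant gain b: multiplies every change by the same positive factor, so the Mann-Whitney ranks do not move.
- Drift d between baseline and week 12: adds d to each change. If the groups share it, it largely cancels between them. In a within-group test it is added in full to the mean change.

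Only drift is a threat, and mainly to the within-group tests.

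**3. Hypothetical sensitivity of a within-group test**

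The documents give no drift and no SD of handgrip change. Both are assumed here. The Protocol's 50 patients per group is used with full retention. The true change is set to zero, and each patient's 12-week window is assumed to contain the same drift d.

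For a paired t-test, two-sided 0.05, 49 degrees of freedom, the noncentrality is d / (SD/√50). With SD 4 kg, SD/√50 = 0.566 kg.

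| SD of change (kg) | Drift d (kg) | Noncentrality | Probability of p < 0.05 |
|---|---|---|---|
| 4 | 0.1 | 0.177 | 5.3% |
| 4 | 0.25 | 0.442 | 7.2% |
| 4 | 0.5 | 0.884 | 14% |
| 4 | 1.0 | 1.768 | 41% |
| 4 | 1.5 | 2.652 | 74% |
| 3 | 1.0 | 2.357 | 64% |
| 5 | 1.0 | 1.414 | 28% |

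The nominal rate is 5%. The table shows how sensitive the test is to drift; it is not evidence that any occurred.

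**4. Coverage of the secondary outcomes in the SAP**

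| Secondary outcome | Between-group comparison of change named | Within-group pre-post test |
|---|---|---|
| Muscular functionality (HGS) | Yes, Mann-Whitney | Yes |
| Body composition (impedance) | No | Only test described that could cover it |

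Body weight is on the between-group list, but it is not an impedance measurement and does not stand in for body composition.

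**The case against.** A reader might infer that neither handgrip nor reactance was validly calibrated. The documents do not support that. If the sentence is misplaced, capacitors of known value were used on the impedance device, and the reactance half of the inference fails. The text is also an account of conduct in the past tense with a visible drafting fault. It shows that no force check is described, not that none was done.

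A reader might also take the drift percentages as the size of a bias in this trial. They are not. No drift is reported for either device, the SD is assumed, and small drifts leave the error rate near nominal. If enrolment was staggered (no enrolment period is given), the same shift in every patient requires steady drift throughout: 1.0 kg per 12 weeks is 1.0 × 52/12 = 4.3 kg per year, which someone would probably notice. A one-time step would touch only patients whose window spans it.

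The stakes are limited further. The rule of "using the same device in order to avoid interobserver and interdevice variability" and random allocation largely protect the HGS comparison between groups, and the affected outcomes are secondary. No outcome or formula based on Xc is named, so the consequence of an unchecked Xc cannot be stated.

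All of this stands. It reduces the calibration wording, taken alone, to a near-clerical correction for completed measurements. It can also be said that within-group tests are weak evidence of a treatment effect even with perfect calibration. That is true, and for body composition it strengthens the point, since no between-group comparison of change is named there.

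**Conclusion.** The point holds in a limited form. The check stated for the dynamometer cannot verify force, and no valid force check is described on either reading. An Xc check is described only if the sentence belongs to the impedance device, which is probable but not settled.

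The consequence that matters for the analysis is in the SAP. The HGS comparison between groups is largely safe, given a single device and randomised groups measured over the same period. Body composition is left with within-group tests, which absorb drift and time trends in full. No actual bias can be quantified. The range of 5.3% to 74% at SD 4 kg depends on an assumed steady drift of 0.1 to 1.5 kg, an assumed SD and full retention, and should be cited only as a hypothetical. The primary outcome and the sample size are not affected.

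**What to change.** 1. **Protocol, Muscle strength and Body composition.** Assign the resistor-and-capacitor sentence to the device it refers to. If that is the impedance analyser, move it there, so that checks of both R and Xc are on record. If it is not, say whether Xc was checked.
2. **Protocol, Muscle strength.** State what force check of the dynamometer was done. If none can be documented, drop the calibration claim for handgrip. If measurement continues, check the dynamometer against known weights and record the results.
3. **SAP.** Add body composition to the variables whose change from baseline is compared between groups, as is already done for HGS. Base conclusions on both secondary outcomes on that comparison, and label the within-group tests as descriptive.

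Cost: a few sentences of text and one further comparison on data already collected. Known weights and a few minutes per check are needed only if measurement is still under way.

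### The unadjusted rank test on change in intake leaves precision unused: neither baseline intake nor V-VST viscosity level enters as a covariate

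*Protocol*

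**What the plan says.** The protocol's opening paragraph on eligibility has the V-VST done at inclusion "in order to evaluate the safety and efficacy of swallowing and confirm the diagnosis of OD" and also to "select the type of viscosity and volume appropriate for the prescription of the texture-modified diet". Since it forms part of eligibility, a result should exist for every patient in both arms before treatment starts.

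Under Nutritional intervention, within the account of the intervention menus (nectar or pudding), the protocol says "The viscosity of the diet was prescribed according to the viscosity and volume tolerated in the V-VST". Controls "received a traditional modified texture diet, with pureed foods and one viscosity of thickened drinks", and of these it adds "The viscosity beverages were not systematically controlled". Allocation is blocked, and no stratification factor is named. The primary outcome is energy (kcal/kg) and protein (g/kg) consumed.

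The SAP (Statistical analysis) tests baseline differences and then forms changes from baseline to the end of the intervention in oral intake, body weight and handgrip strength. Between groups these changes "were compared with the Mann-Whitney U test", and the reason given is that the data are not normally distributed. It names no covariate, stratified test or regression model, does not mention the V-VST, and plans no between-group effect estimate with a confidence interval. Missing values are imputed in five data sets and the results pooled.

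**The concern.** Two pre-treatment measurements are on file and could sharpen the comparison of the primary outcome. A change score uses baseline intake with its coefficient fixed at 1, which is inefficient unless baseline and final values are very highly correlated. V-VST level describes how a patient swallows and decides the form of diet given in the intervention arm. It could plausibly relate to how much is eaten, yet neither the allocation nor the analysis uses it.

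The stake is the width of the interval around the intake difference. The sample size was justified on mortality, so the documents show no power for intake, and any cheap gain in precision is worth having. A rank test alone also gives the reader a p-value but no difference in kcal/kg or g/kg.

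**Working it through.** **Inputs from the documents.** 50 patients per arm; change from baseline compared by Mann-Whitney U; V-VST on all patients at inclusion. The plan's own figure, "We estimated a sample size of 50 patients per group" "with an alpha level of 0.05 and more than 90% power to detect a difference of 15% of mortality between groups", cannot be reproduced because control mortality and sidedness are not given. At an assumed 5% v 20%, two-sided, 90% power, a comparison of proportions needs 101 per arm. That figure concerns mortality, so only the 50 per arm is used below.

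**Assumed, because the documents give no values.** Equal intake variance (set to 1) at baseline and end; baseline-final correlation w of 0.3, 0.5 or 0.7; half the patients at each V-VST level; a difference d in mean intake between levels of 0.3, 0.5 or 0.8 SD. The variances refer to mean differences and stand in for the rank test's precision.

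**Step 1: change score against baseline adjustment.** Variance of change = 2(1-w). Residual variance of final intake given baseline = 1-w². The ratio is (1+w)/2, so the saving is (1-w)/2.

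| w | 2(1-w) | 1-w² | Saving | Equivalent n per arm |
|---|---|---|---|---|
| 0.3 | 1.40 | 0.91 | 35% | 50/0.65 = 76.9 |
| 0.5 | 1.00 | 0.75 | 25% | 50/0.75 = 66.7 |
| 0.7 | 0.60 | 0.51 | 15% | 50/0.85 = 58.8 |

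**Step 2: adding V-VST level when it shifts baseline and final intake equally.** Take w now as the correlation within a level, and q = 0.25d² (0.0225, 0.0625, 0.16). In a change score the level effect cancels, so level adds nothing there. With arm and baseline in the model:

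- without level, residual variance = (1+q) - (w+q)²/(1+q) = (1-w)(1+w+2q)/(1+q);
- with level, residual variance = 1-w²;
- further saving = q(1-w)/(1+w+2q).

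| | d=0.3 | d=0.5 | d=0.8 |
|---|---|---|---|
| w=0.3 | 1.2% | 3.1% | 6.9% |
| w=0.5 | 0.7% | 1.9% | 4.4% |
| w=0.7 | 0.4% | 1.0% | 2.4% |

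Example: d=0.5, w=0.5 gives 0.0625×0.5/(1.5+0.125) = 0.0192. In this set-up the full model saves exactly (1-w)/2 against change, here 25%. Baseline alone supplies (1-w)/[2(1+q)] = 0.5/2.125 = 23.5%.

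**Step 3: if level predicts change in intake.** Let r be the correlation between level and change (assumed). Adjusting change for level cuts its variance by r². For an effect of 0.56 SD, which has 80% power unadjusted at 50 per arm, power becomes 81.6% (r=0.2), 83.6% (r=0.3) or 89.9% (r=0.5). In 2,000 simulated trials with normal data at r=0.3, power was 77.7% for Mann-Whitney, 80.4% for an unadjusted linear model and 83.1% with level added. So about half of that 5.4-point gap is due to the rank test on normal data, not to V-VST.

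**Step 4: chance imbalance.** The SD of the difference between arms in the share at one level is sqrt(2×0.25/50) = 0.10. A difference of at least 15 points has a probability of about 13%. At r=0.3 the levels differ by 0.3/0.5 = 0.6 SD in change, so a 15-point imbalance moves that trial's estimate by 0.15×0.6 = 0.09 SD.

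**The case against.** The strongest reply is that the plan is valid as it stands. Randomisation already allows for chance imbalance in any covariate, and the unadjusted test keeps its error rate. Analysing change removes any stable intake difference between V-VST levels. No statement in either document says that nectar v pudding grades severity or predicts intake. The prescription also used tolerated volume, which a two-level covariate drops. Supplements for low intake in both arms could weaken any link further, if they count as intake, which is not stated. The SAP gives non-normality as its reason for a rank test. All of this stands, and it limits the point to precision.

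A reader might infer three stronger things.

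- **That the comparison is biased because V-VST imbalance is left uncorrected.** It is not: imbalance adds random error to the single estimate, as in step 4.
- **That V-VST level decides the diet in both arms.** The documents describe this for the intervention menus only; controls had one drink viscosity, not systematically controlled.
- **That adjusting for V-VST recovers its full share of intake variance.** That share is q/(1+q), or 2%, 6% and 14% for d of 0.3, 0.5 and 0.8. It applies to a single intake measurement with no baseline in play, which is neither the SAP's analysis nor the one proposed here.

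The reply does not answer the point on baseline intake. Subtraction is a less efficient use of it than adjustment, and a rank test alone yields no adjusted difference.

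**Conclusion.** The point holds as a cheap improvement in precision, not as an error in the plan. Moving from change scores to adjustment for baseline intake would cut the variance by about 15% to 35% if the baseline-final correlation lies between 0.7 and 0.3. V-VST level adds about 0.4% to 7% more under equal shifts at both visits, and this may be negligible in practice. A larger V-VST gain needs level to predict change in intake, for which the documents offer no evidence. All sizes rest on assumed correlations, level differences and a 50:50 split, equal variances at the two visits, and no loss to dropout.

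**What to change.** For energy (kcal/kg) and for protein (g/kg), compare final intake between arms with a linear model containing arm, baseline intake and V-VST tolerated viscosity (nectar v pudding). Report the adjusted difference with its 95% CI, pooled over the five imputed data sets, and include V-VST level in the imputation model. Because the SAP cites non-normal data, use robust or bootstrap standard errors and keep the Mann-Whitney test on change as a sensitivity analysis.

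Both documents are written in the past tense. If results have already been seen, label the adjusted model post hoc.

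The cost is a few sentences in the SAP and about two degrees of freedom out of 98 (100 patients less two arm means). No new data are needed, provided the V-VST result was kept for controls as well as intervention patients.

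### Supplements are prescribed on the scale of the primary outcome, but the plan does not say whether they count and reports none by arm, so neither a null nor a positive result can be attributed to the diet

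*Protocol*

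**What the plan says.** The outcome paragraph of the Protocol (end of the Nutritional intervention section) reads: "The primary outcome was the amount of energy (kcal/kg) and protein (g/kg) consumed". The Dietary intake section names the instrument: "For the evaluation of the quality and quantity of dietary intake, a 24-hour multiple-step recall was applied".

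The same paragraph on outcomes sets an adherence check: "Adherence to the prescribed meal plan was evaluated at each visit", and to count as adherent "it was necessary to have an intake of more than 80% of the nutritional requirements with 24-hour recall". It then gives the supplement rule: "If the intake was lower than indicated, oral nutritional supplements were prescribed to meet the nutritional requirements established in both groups". On timing it says: "The follow-up was carried out in 5 visits during 12 weeks". Requirements are calculated the same way in both arms: 25-30 kcal/kg and 1.2-1.5 g/kg protein for BMI below 30, and 20-25 kcal and 2 g protein per kg ideal weight for BMI above 30.

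The SAP says that "changes between baseline and final intervention in oral intake, body weight and HGS were obtained between groups" and that these "were compared with the Mann-Whitney U test, according to the nonparametric distribution of the data". It has an intention-to-treat set and a per-protocol set, the latter defined by finishing follow-up. Supplements are not mentioned in the SAP.

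**The concern.** The supplement trigger, the supplement target and the primary outcome are all amounts of intake, and the trigger and the dietary assessment both use a 24-hour recall. A patient with low intake is prescribed energy and protein, which are the quantities being compared. The arms differ in texture, viscosity and bolus volume, and the question is whether that difference raises intake.

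If supplements count as consumed, the arm with the larger food shortfall is prescribed more and total intake converges. An ineffective diet and successful supplementation of the control arm then look alike. A positive difference has the matching problem: it can arise because one arm took more of its prescribed supplement. If supplements do not count, they may still replace food and alter the recall. Nothing planned separates these explanations, and neither analysis set is defined by supplement use.

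**Working it through.** **Figure in the plan.** There is none to reproduce. The 50 per group was derived from a mortality difference, and the documents give no expected intake, SD or supplement uptake.

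**Inputs from the documents.** Energy requirement R (25-30 kcal/kg, or 20-25 kcal/kg ideal weight for BMI above 30, midpoint 22.5); the 80% threshold, read here as the supplement trigger; 50 per group; Mann-Whitney test on change.

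**Assumed inputs.** Supplements are counted and prescribed up to R. Control food intake is normal with mean m of 17 to 24 and SD s of 5 to 7 kcal/kg. The food difference is 4.0 kcal/kg. A mean share u of each prescribed gap is taken, equal in both arms.

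**Formula.** The mean gap prescribed is T(m) = E[(R - X) when X ≤ 0.8R] = (R - m)Φ(z) + s·φ(z), with z = (0.8R - m)/s. The total-intake contrast is 4.0 + u[T(m+4) - T(m)].

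**One case by hand** (R = 27.5, trigger 22, m = 20, s = 6):
- Control: z = 0.333, T = 7.5 × 0.6306 + 6 × 0.3774 = 6.99.
- Intervention: z = -0.333, T = 3.5 × 0.3694 + 6 × 0.3774 = 3.56.
- Contrast: 4.0 - 0.5 × 3.44 = 2.28 at half uptake, and 4.0 - 3.44 = 0.56 at full uptake.

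**Contrast over the grid** (m = 17, 18, 20, 22, 24; s = 5, 6, 7), kcal/kg:

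| R | u = 0.10 | u = 0.25 | u = 0.50 | u = 1.00 |
|---|---|---|---|---|
| 22.5 | 3.69 to 3.93 | 3.23 to 3.84 | 2.47 to 3.67 | 0.94 to 3.35 |
| 25 | 3.62 to 3.87 | 3.04 to 3.68 | 2.08 to 3.36 | 0.17 to 2.73 |
| 27.5 | 3.57 to 3.79 | 2.92 to 3.47 | 1.84 to 2.93 | -0.32 to 1.87 |
| 30 | 3.55 to 3.71 | 2.87 to 3.29 | 1.75 to 2.57 | -0.51 to 1.15 |

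For protein (R = 1.35 g/kg, assumed food difference 0.20, m 0.8 to 1.1, SD 0.25 to 0.35), the contrast is 0.09 to 0.13 at half uptake and -0.02 to 0.07 at full uptake.

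**Power on change from baseline** (simulation; R = 27.5, s = 6, baseline-final correlation 0.5, no supplements at baseline, 50 per group, two-sided 0.05):

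| Control mean | Food only | Half uptake, each fills half the gap | Half uptake, all or none | Full uptake |
|---|---|---|---|---|
| 18 | 0.89 | 0.46 | 0.29 | 0.05 |
| 20 | 0.89 | 0.53 | 0.38 | 0.07 |
| 24 | 0.89 | 0.71 | 0.64 | 0.32 |

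With no food difference and equal uptake, the rejection rate stays near 0.05.

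**Unequal uptake, no food difference.** With 75% uptake in one arm and 50% in the other, the contrast is (0.75 - 0.50) × T(m). At R = 27.5 and s = 6, T(18) = 9.02 and T(24) = 3.56, giving 2.3 and 0.9 kcal/kg.

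**Displacement** (R = 27.5, m = 20, s = 6, full uptake). Let a share dC of supplement energy replace food in control and dI in intervention. Diet-only contrast = 4.0 - (dI × 3.56 - dC × 6.99). Total contrast = 4.0 + (1 - dI) × 3.56 - (1 - dC) × 6.99.
- 20% in both arms: diet-only 4.7, total 1.3. The two lie either side of 4.0.
- 20% in control and 60% in intervention: diet-only 3.3, total -0.2. Both lie below 4.0.

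**The case against.** The strongest reply is that diet plus a common supplement rule is a legitimate strategy and that randomisation protects its comparison. That stands. A reader might infer that the supplement rule makes the primary comparison invalid. The documents do not support this: the rule is the same in both arms and the contrast of the two strategies is sound. What is missing is a statement that this is the effect estimated.

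Second, the outcome may be food only. The recall is described as measuring dietary intake, and adherence refers to the meal plan, so it cannot be taken as fact that supplements enter the outcome. If they do not, the attenuation and power figures fall away and displacement is what remains. This stands, and it is why the SAP should say how supplements were handled rather than be told to count them.

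Third, the figures rest almost wholly on assumptions. Attenuation is mild at low uptake and at the lower requirement for BMI above 30. The power loss at half uptake also depends on the scale: on final intake alone, if every triggered patient fills half the gap, power is still 0.86 to 0.88, because the spread shrinks with the difference. The SAP tests change, where the baseline spread remains. The model also lets the final recall trigger its own top-up. Triggering from an earlier visit instead does not raise power on change, and it lowers the final-intake figure to 0.46 to 0.72.

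Fourth, the documents are dated 2021 and written in the past tense, so the additions are probably post hoc, and no passage says the recalls itemise supplements. Both points limit the remedy without removing the gap.

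**Conclusion.** The concern holds as a gap in outcome definition and reporting that should be closed. As planned, a between-arm difference in intake supports a conclusion about each diet plus the common supplement rule, and none about the diet itself.

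If supplements count, are prescribed up to requirement and are taken equally in both arms, a 4.0 kcal/kg food difference appears as about 1.7 to 3.7 at half uptake and about -0.5 to 3.4 at full uptake, for requirements of 22.5 to 30 kcal/kg. At 10-25% uptake it is 2.9 to 3.9. Power on change falls from about 0.89 to about 0.3-0.7 at half uptake (requirement 27.5, SD 6, correlation 0.5), depending on control mean and uptake pattern. Only the requirement ranges, the 80% threshold, the sample size and the test come from the documents.

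Two further inferences are not supported. One is that only a null result is affected: with no food difference, unequal uptake alone can produce 0.9 to 2.3 kcal/kg, and nothing in the plan shows that uptake is equal. The other is that diet-only and total intake always bracket the diet effect: this can fail when displacement differs between arms.

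**What to change.** Leave the supplement rule unchanged.

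1. State in the SAP whether supplement energy and protein were counted in the primary outcome, following how the recalls were actually coded. If they were, state that the effect estimated is each diet plus the common supplement rule.
2. Add the other version as a supporting analysis (diet only if supplements were counted, total if not), with the same between-group test and analysis sets.
3. Report by arm and visit the proportion prescribed supplements, and the supplement kcal/kg and g/kg consumed.
4. Base any conclusion about the diet, positive or null, on both versions together with supplement use by arm. Note that the two versions bracket the diet effect only if displacement is similar in both arms.

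Label the additions post hoc if data by arm have been seen.

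The cost is coding of supplement items, one extra analysis and one table. If the recalls do not itemise supplements, report only the proportion prescribed by arm and limit the conclusion to diet plus supplement rule.
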